6.2. Preparation/Handling/Storage/Accountability

1. The investigator or designee must confirm appropriate temperature conditions have been maintained during transit for all study interventions received and any discrepancies are reported and resolved before use of the study intervention.
2. Only participants enrolled in the study may receive study intervention and only authorized site staff may supply or administer study intervention. All study interventions must be stored in a secure, environmentally controlled, and monitored (manual or automated recording) area in accordance with the labeled storage conditions with access limited to the investigator and authorized site staff. At a minimum, daily minimum and maximum temperatures for all site storage locations must be documented and available upon request. Data for nonworking days must indicate the minimum and maximum temperatures since previously documented for all site storage locations upon return to business.
3. Any excursions from the study intervention label storage conditions should be reported to Pfizer upon discovery along with any actions taken. The site should actively pursue options for returning the study intervention to the storage conditions described in the labeling, as soon as possible. Once an excursion is identified, the study intervention must be quarantined and not used until Pfizer provides permission to use the study intervention. Specific details regarding the definition of an excursion and information the site should report for each excursion will be provided to the site in the PCRU site procedures.
4. Any storage conditions stated in the SRSD will be superseded by the storage conditions stated on the product label.
5. Study interventions should be stored in their original containers and in accordance with documentation provided to the site.
6. The investigator, institution, or the head of the medical institution (where applicable) is responsible for study intervention accountability, reconciliation, and record maintenance (ie, receipt, reconciliation, and final disposition records), such as the IPAL or sponsor-approved equivalent. All study interventions will be accounted for using a study intervention accountability form/record.
7. Further guidance and information for the final disposition of unused study interventions are provided by CRU or as per local procedures, All destruction must be

adequately documented. If destruction is authorized to take place at the investigator site, the investigator must ensure that the materials are destroyed in compliance with applicable environmental regulations, institutional policy, and any special instructions provided by Pfizer.

Upon identification of a product complaint, notify the sponsor within 1 business day of discovery.

6.2.1. Preparation and Dispensing

Within this protocol, preparation refers to the investigator site activities performed to make the study intervention ready for administration or dispensing to the participant by qualified staff. Dispensing is defined as the provision of study intervention, concomitant treatments, and accompanying information by qualified staff member(s) to a healthcare provider, participant in accordance with this protocol. Local health authority regulations or investigator site guidelines may use alternative terms for these activities.

Ritlecitinib (200 mg, four 50 mg capsules) and tolbutamide (500 mg, provided as one 500 mg tablet) will be prepared at the CRU in the individual dosing containers by 2 operators, 1 of whom is an appropriately qualified and experienced member of the study staff (eg, physician, nurse, physician's assistant, nurse practitioner, pharmacy assistant/technician, or pharmacist). The tablets and capsules will be provided in unit dose containers and labeled in accordance with Pfizer regulations and the clinical site's labeling requirements.

6.3. Measures to Minimize Bias: Randomization and Blinding

6.3.1. Allocation to Study Intervention

The investigator's knowledge of the treatment should not influence the decision to enroll a particular participant or affect the order in which participants are enrolled.

The investigator will assign participant numbers to the participants as they are screened for the study. Pfizer will provide a randomization schedule to the investigator site and, in accordance with the randomization numbers, the participant will receive the study treatment regimen assigned to the corresponding randomization number.

6.4. Study Intervention Compliance

Participants will receive study intervention directly from the investigator or designee, under medical supervision. The date and time of each dose administered in the clinic will be recorded in the source documents and recorded in the CRF. The dose of study intervention and study participant identification will be confirmed at the time of dosing by a member of the study site staff. The oral cavity of each participant will be examined following dosing to ensure the investigational product was taken.

6.5. Dose Modification

Dose modification is not allowed in the current study.

6.6. Continued Access to Study Intervention After the End of the Study

No intervention will be provided to study participants at the end of their study participation.

6.7. Treatment of Overdose

For this study, any dose of ritlecitinib greater than 800 mg within a 24-hour time period will be considered an overdose.

Any dose of tolbutamide greater than 3000 mg within a 24-hour time period will be considered an overdose.

There is no specific antidote or specific treatment for an overdose of ritlecitinib. For tolbutamide, investigators should consider the treatment of overdose as per USPI.⁵

In the event of an overdose, the investigator should:

1. Contact the medical monitor immediately.
2. Closely monitor the participant for any AEs/SAEs and laboratory abnormalities until ritlecitinib and tolbutamide can no longer be detected systemically (at least 2 days).
3. Document the quantity of the excess dose as well as the duration of the overdose in the CRF.
4. Overdose is reportable to Pfizer Safety **only when associated with an SAE**.
5. Obtain a blood sample for PK analysis within 4 days from the date of the last dose of study intervention if requested by the medical monitor (determined on a case-by-case basis).

Decisions regarding dose interruptions or modifications will be made by the investigator in consultation with the medical monitor based on the clinical evaluation of the participant.

6.8. Concomitant Therapy

Use of prescription or nonprescription drugs and dietary and herbal supplements are prohibited within 7 days or 5 half-lives (whichever is longer) prior to the first dose of study intervention. Limited use of nonprescription medications that are not believed to affect participant safety or the overall results of the study may be permitted on a case-by-case basis following approval by the sponsor. Acetaminophen/paracetamol may be used at doses of ≤ 3 g/day. Ibuprofen may be used at doses ≤ 1200 mg/day.

Systemic therapy with any of the medications that are moderate or strong CYP2C9 inhibitors or moderate or strong CYP2C9 inducers within 28 days or 5 half-lives (whichever is longer) are prohibited prior to the first dose of investigational product.

Females using hormonal contraceptives or taking HRT may be eligible to participate in this study if they are willing to discontinue therapy at least 28 days prior to the first dose of study treatment and remain off hormonal therapy for the duration of the study. Depo-Provera® must be discontinued at least 6 months prior to the first dose of study treatment. Note that another approved method of contraception must then be used ([Section 10.4.3](#)).

All concomitant treatments taken during the study must be recorded with indication, daily dose, and start and stop dates of administration. Concomitant drug and non-drug treatment will be collected. All participants will be questioned about concomitant treatment at each clinic visit.

Treatments taken within 28 days before the first dose of investigational product will be documented as a prior treatment. Treatments taken after the first dose of investigational product will be documented as concomitant treatments.

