9. Participants who, according to the product label for tolbutamide, would be at increased safety risk if dosed with tolbutamide.
10. History of hypersensitivity to tolbutamide or any of its excipients.

11. Other medical or psychiatric condition (including recent [within the past year] or active suicidal ideation/behavior, laboratory abnormality, or other conditions or situations related to COVID-19 pandemic [eg, contact with a positive case, residence, or travel to an area with high incidence]) that may increase the risk of study participation or, in the investigator's judgment, make the participant inappropriate for entry into this study.
12. Known glucose 6-phosphate dehydrogenase (G6PD) deficiency.

Prior/Concomitant Therapy:

13. Use of prescription or nonprescription drugs and dietary supplements within 7 days or 5 half-lives (whichever is longer) prior to Day 1. Limited use of nonprescription medications that are not thought to affect participant safety or the overall results of the study may be permitted on a case by case basis following approval by the sponsor.

Herbal supplements, hormonal contraceptives and HRT must be discontinued at least 28 days prior to the first dose of investigational product; Depo-Provera® and SAYANA® PRESS must be discontinued at least 6 months prior to dosing of investigational product.

14. Systemic therapy with any of the medications that are moderate or strong CYP2C9 inhibitors within 28 days or 5 half-lives (whichever is longer) or moderate or strong CYP2C9 inducers within 28 days or 5 half-lives (whichever is longer) prior to the first dose of investigational product ([Section 6.8](#)).
15. Vaccination with a live attenuated vaccine within 6 weeks prior to the first dose of study intervention (refer to [Section 5.3.5](#) for additional details).

Prior/Concurrent Clinical Study Experience:

16. Previous administration of investigational products (eg, drugs or vaccines) within 30 days (or as determined by the local requirement) or 5 half-lives preceding the first dose of investigational product used in this study (whichever is longer).
17. Known participation in a clinical trial of ritlecitinib and the participant experienced a ritlecitinib-related AE that led to discontinuation or had a ritlecitinib-related SAE.

Diagnostic Assessments:

18. A positive urine drug test.
19. A positive pregnancy test.

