5.3.1. Meals and Dietary Restrictions

- Participants must abstain from all food and drink (except water) at least 12 hours prior to any safety laboratory evaluations.
- Noncaffeinated drinks (except grapefruit or grapefruit-related citrus fruit juices, see below) may be consumed with meals and the evening snack.
- On PK days (Period 1 Day 1 and Period 2 Day 10), participants should begin breakfast approximately 30 minutes prior to tolbutamide administration. The breakfast will be consumed over approximately a 20-minute interval with tolbutamide administered within approximately 10 minutes of completion of the meal. Participants will be encouraged to complete the entire breakfast. There are no water restrictions prior to and after dosing. No restriction will be placed on breakfast on other study days provided other restrictions are followed.
- On PK days (Period 1 Day 1 and Period 2 Day 10), lunch will be provided approximately 4 hours after tolbutamide dosing. Food restrictions only apply on the days when tolbutamide is dosed.
- On PK days (Period 1 Day 1 and Period 2 Day 10), dinner will be provided approximately 9 to 10 hours after tolbutamide dosing. Food restrictions only apply on the days when tolbutamide is dosed.
- An evening snack is permitted.
- Participants will refrain from consuming red wine, grapefruit, or grapefruit-related citrus fruits (eg, Seville oranges, pomelos, fruit juices) from 7 days prior to the first dose of investigational product until collection of the final PK blood sample.
- While participants are confined, their total daily nutritional composition should be approximately 55% carbohydrate, 30% fat, and 15% protein. The daily caloric intake per participant should not exceed approximately 3200 kcal.

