## **5.7. Protocol Deviations**

Participants who experience events that may affect their PK profile (eg lack of compliance with dosing) may be excluded from the PK analysis. At the discretion of the pharmacokineticist a concentration value may also be excluded if the deviation in sampling time is of sufficient concern or if the concentration is anomalous for any other reason.

A full list of protocol deviations will be compiled and reviewed to identify major and minor deviations prior to database closure.

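### Does the lack of an on-study limit on CYP2C9 inhibitors and inducers leave the tolbutamide ratio open to contamination?

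*Protocol*

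**What the plan says.** Exclusion criterion 14 (Protocol Section 5.2) bars moderate and strong CYP2C9 inhibitors, and it bars "inducers within 28 days or 5 half-lives (whichever is longer) prior to the first dose of investigational product". Section 6.8 repeats the window and closes it at the same point: "whichever is longer) are prohibited prior to the first dose of investigational product". Tolbutamide is itself an investigational product (Section 6.1), so that point is Period 1 Day 1, which is the Reference measurement.

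Other restrictions carry an on-study window. Grapefruit and red wine are barred "from 7 days prior to the first dose of investigational product until collection of the final PK blood sample" (Section 5.3.1). Women who stop hormonal therapy must "remain off hormonal therapy for the duration of the study" (Section 6.8). Live vaccines are barred during the study as well as before and after it (Section 5.3.5).

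On herbal products the two sections differ. Exclusion 13 says "Herbal supplements, hormonal contraceptives and HRT must be discontinued at least 28 days prior to the first dose of investigational product". Section 6.8, also counting back from initial dosing, has a shorter window: "Use of prescription or nonprescription drugs and dietary and herbal supplements are prohibited within 7 days or 5 half-lives (whichever is longer) prior to".

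On data handling, SAP Section 5.7 is permissive: "Participants who experience events that may affect their PK profile (eg lack of compliance with dosing) may be excluded from the PK analysis". SAP Section 7.3 is mandatory. A participant's PK parameter estimate known to be biased is footnoted and left out of both the summary statistics and the statistical analyses. Vomiting is given there only as an example.

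**The concern.** The primary endpoint is a within-participant ratio of exposure to a drug cleared mainly by CYP2C9. The sequence is fixed and the model has only treatment and participant terms (Protocol Section 9.3.2; SAP Section 6.4 lists no covariates). A CYP2C9 modulator started after the Period 1 profile would therefore be indistinguishable from a ritlecitinib effect. The restriction stops at the point where such a drug would begin to do harm.

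There is a conceivable route. Infection is a named ritlecitinib risk (Section 2.3.1). Section 10.8.2 requires withdrawal for serious infections, so a participant with a milder, treated infection could reach the Day 10 profile. Section 6.8.1 calls for supportive care of adverse events and sets no CYP2C9 limit. Such use would breach no stated prohibition, so a deviation review need not flag it. If SAP Section 5.7 were the only rule, keeping or dropping the data would be discretionary.

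**Working it through.** **Uncovered interval.** Period 1 Day 1 to Period 2 Day 1 is 3 days, Period 2 Day 1 to Day 10 is 9 days, and the last sample is 36 hours later: 3 + 9 + 1.5 = 13.5 days. Confinement runs from Period 1 Day -1 to Period 2 Day 12 (Section 1.3), so it covers the whole interval.

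**The plan's own precision figure.** Inputs from Section 9.5: n = 12, within-participant SD 0.20 on the log scale, 90% interval.

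- Plain expected half-width: t(0.95, 11) × 0.20 × √(2/12) = 0.1466, giving 86.4-115.8 around 100%. This is not Table 5, which gives 84.4-118.4.
- Multiplying by √(χ²(0.80, 11)/11) gives 0.1691, and all eight rows of Table 5 then match. Table 5 therefore appears to carry an 80% assurance on the half-width, although the protocol does not say so.

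**Shift from one affected participant, drug active in Period 2 only.** The ratio is multiplied by fold^(1/n).

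| Effect on AUC | 1 of 12 | 1 of 10 |
|---|---|---|
| Inducer, clearance × 1.92 (Section 4.3.2) | 0.947 | 0.937 |
| Inhibitor, AUC × 1.5 (assumed) | 1.034 | 1.041 |
| Inhibitor, AUC × 2 (assumed) | 1.059 | 1.072 |
| Inhibitor, AUC × 5 (assumed) | 1.144 | 1.175 |

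The documents give no inhibitor effect size, so the last three rows are a range only.

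**Widening if the value were kept.** The expected variance of the differences is 2 × 0.20² + δ²/12.

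- δ = ln 1.92 = 0.652: 0.080 + 0.0355 = 0.1155; half-width t(0.95, 11) × √(0.1155/12) = 0.176.
- δ = ln 2 = 0.693: 0.080 + 0.0400 = 0.1200; half-width 0.180.

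Before any shift, that is about 84 to 119 or 120 around 100%. With the shift, a true 100% under the inducer reads 94.7% (79.4-113.0). A true 80% under the 2-fold inhibitor reads 84.8% (70.8-101.4).

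**Result if the value is removed, as SAP Section 7.3 directs.** Eleven pairs remain: t(0.95, 10) × 0.20 × √(2/11) = 0.1546, giving 85.7-116.7 around 100%. The shift disappears, the width rises from 29.4 to 31.0 points, and the study stays above its minimum of 10 evaluable participants.

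**Would the bias be known?** Indication, daily dose, and start and stop dates are recorded for every concomitant treatment (Section 6.8). Treatments are assessed throughout confinement (Section 1.3) and listed (SAP Section 8.3.9). Significant deviations are reviewed before database closure (SAP Section 5.7.2). Model residuals are inspected, with analyses excluding outliers available (SAP Section 8.2). The SD of one within-participant difference is 0.20 × √2 = 0.283, so a shift of 0.652 is about 2.3 SDs. That is visible on a plot, though not certain to stand out; the medication record is the firmer evidence.

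**Herbal windows.** Both lie wholly before the first dose, so they say nothing about drugs taken between the two profiles. Entry requires all the Section 5.2 criteria, and Section 5 allows no waivers. A participant who meets the 28-day window also meets the 7-day one, and the half-life condition still applies as written.

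**The case for a change.** The strongest case for a change is that silence here is hard to read as deliberate, because the protocol writes an on-study window for grapefruit, hormonal therapy and live vaccines. The sponsor-approval clause in Section 6.8 covers nonprescription drugs only, so it does not reach a prescription given for an adverse event. SAP Section 7.3 does not name concomitant drugs, say who decides, or say when. SAP Section 5.7 uses a weaker verb for what could be the same case. With 12 participants, one kept value can lift a true 80% to an interval that includes 100%, and so blur the induction the study is meant to estimate. Clearer wording would cost almost nothing.

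The textual observations all stand, and so does the arithmetic on its assumptions. Three steps to the conclusion do not:

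- No passage allows such a drug on study; that is inferred from silence. The approval clause and the stated acetaminophen and ibuprofen limits point to intended control.
- SAP Section 7.3 does force out a known biased estimate, and it does not depend on a deviation having been declared. A recorded modulator of the probe's main pathway fits it closely, although some judgement remains.
- The sizes are severe cases. The inducer row takes the full effect of an agent the protocol calls potent, while Section 4.3.1 notes that induction takes several days to appear. The 86.4-115.8 comparator is narrower than the protocol's own 84.4-118.4, and the contaminated interval of about 84 to 119 is close to the latter. That comparison is not like for like if Table 5 carries an assurance margin, but it shows that the planned precision already allowed for this much spread.

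**Conclusion.** The restriction does lack an on-study end, but followed as written the plan would still give a sound estimate. Exposure is unlikely in healthy participants who stay in the unit from before the first dose until after the last sample. If it happened it would be on record, and SAP Section 7.3 would take the affected estimate out at a cost of about 1.6 points of interval width. If the value were wrongly kept, one of 12 participants would move the ratio by -5.3% (inducer at the protocol's figure) or by +3.4% to +14.4% (inhibitor assumed at 1.5-fold to 5-fold). That would enter an estimation study with no hypothesis or decision rule (SAP Sections 4.1 and 4.2).

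The conclusion rests on two assumptions: the pharmacokineticist treats recorded use of a moderate or strong CYP2C9 modulator as a known bias, and at most one or so participants are affected. What rule should govern such drugs on study is a clinical matter for the sponsor, and this review takes no position on it. The herbal windows in Sections 5.2 and 6.8 disagree and must be reconciled as a clerical matter. That mismatch falls before the first dose and does not touch the analysis.

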6.8.1. Rescue Medicine

There is no specific rescue therapy to reverse the AEs caused by ritlecitinib or tolbutamide; standard medical supportive care must be provided to manage the AEs.

7. DISCONTINUATION OF STUDY INTERVENTION AND PARTICIPANT DISCONTINUATION/WITHDRAWAL

7.1. Discontinuation of Study Intervention

It may be necessary for a participant to permanently discontinue study intervention. Reasons for permanent discontinuation of study intervention include the following as outlined in [Section 10.8.2](#).

If study intervention is definitively discontinued, the participant will not remain in the study for further evaluation. See the [SoA](#) for data to be collected at the time of discontinuation of study intervention.

See [Appendix 8](#) for guidelines for safety monitoring and discontinuation guidelines.

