7.2. Participant Discontinuation/Withdrawal From the Study

A participant may withdraw from the study at any time at his/her own request. Reasons for discontinuation from the study include the following:

- Refused further follow-up;
- Lost to follow-up;
- Death;
- Study terminated by sponsor;

- At the discretion of the investigator for behavioral, compliance, or administrative reasons.

At the time of discontinuing from the study, if possible, an early discontinuation visit should be conducted. See the [SoA](#) for assessments to be collected at the time of study discontinuation and follow-up and for any further evaluations that need to be completed.

The early discontinuation visit applies only to participants who are enrolled/randomized and then are prematurely withdrawn from the study. Participants should be questioned regarding their reason for withdrawal.

The participant will be permanently discontinued both from the study intervention and from the study at that time.

If a participant withdraws from the study, he/she may request destruction of any remaining samples taken and not tested, and the investigator must document any such requests in the site study records and notify the sponsor accordingly.

If the participant withdraws from the study and also withdraws consent (see Section 7.2.1 for disclosure of future information, no further evaluations should be performed and no additional data should be collected. The sponsor may retain and continue to use any data collected before such withdrawal of consent.

Lack of completion of all or any of the withdrawal/early termination procedures will not be viewed as protocol deviations so long as the participant's safety was preserved.

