7.2.1. Withdrawal of Consent

Participants who request to discontinue receipt of study intervention will remain in the study and must continue to be followed for protocol-specified follow-up procedures. The only exception to this is when a participant specifically withdraws consent for any further contact with him or her or persons previously authorized by the participant to provide this information. Participants should notify the investigator in writing of the decision to withdraw consent from future follow-up, whenever possible. The withdrawal of consent should be explained in detail in the medical records by the investigator, as to whether the withdrawal is only from further receipt of study intervention or also from study procedures and/or posttreatment study follow-up, and entered on the appropriate CRF page. In the event that vital status (whether the participant is alive or dead) is being measured, publicly available information should be used to determine vital status only as appropriately directed in accordance with local law.

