8.3.1. Time Period and Frequency for Collecting AE and SAE Information

The time period for actively eliciting and collecting AEs and SAEs (“active collection period”) for each participant begins from the time the participant provides informed consent, which is obtained before the participant’s participation in the study (ie, before undergoing any study-related procedure and/or receiving study intervention), through and including a minimum of 28 calendar days, after the last administration of the study intervention.

Follow-up by the investigator continues throughout and after the active collection period and until the AE or SAE or its sequelae resolve or stabilize at a level acceptable to the investigator.

For participants who are screen failures, the active collection period ends when screen failure status is determined.

If the participant withdraws from the study and also withdraws consent for the collection of future information, the active collection period ends when consent is withdrawn.

If a participant definitively discontinues or temporarily discontinues study intervention because of an AE or SAE, the AE or SAE must be recorded on the CRF and the SAE reported using the CT SAE Report Form.

Investigators are not obligated to actively seek information on AE or SAE after the participant has concluded study participation. However, if the investigator learns of any SAE, including a death, at any time after a participant has completed the study, and he/she

considers the event to be reasonably related to the study intervention, the investigator must promptly report the SAE to Pfizer using the CT SAE Report Form.

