10.8.2. Participant Discontinuation Criteria

Treatment will be discontinued and the participant withdrawn from this study for:

Adverse Events:

- Serious infections, defined as any infection (viral, bacterial, and fungal) requiring parenteral antimicrobial therapy or hospitalization for treatment or meeting other criteria that require the infection to be classified as serious adverse event;
- Treatment-related SAEs;
- Other serious or severe AEs, at the discretion of the investigator or sponsor.

ECG Findings:

- Confirmed QTcF >500 milliseconds;
- Confirmed increase from baseline in QTcF of >60 milliseconds.

Laboratory Abnormalities:

- All the following laboratory abnormalities require discontinuation if they are confirmed by retest. Refer to the re-testing timeframes for laboratory abnormalities in [Section 10.8.1](#).
 - ANC <750/mm³ (<0.75 × 10⁹/L);
 - Hemoglobin <9.0 g/dL (<5.59 mmol/L or <90 g/L) or a decrease of >30% from baseline (either criterion or both);
 - Platelet count <75,000/mm³ (<75.0 × 10⁹/L);
 - ALC <500/mm³ (<0.5 × 10⁹/L).

NOTE: Participants with ALC <500/mm³ (0.5 × 10⁹/L) will be reflex tested for FACS-TBNK until the ALC resolves or stabilizes at a level acceptable to the investigator and sponsor.

- Creatine kinase >10 × ULN.

NOTE: In addition to re-testing creatinine kinase >3 × ULN, urine myoglobin will be performed as reflex testing for any participant with creatine kinase >10 × ULN.

- AST or ALT that meet ANY of the following:
 - >3 times ULN with at least one total bilirubin value >2 times ULN;
 - >3 times ULN accompanied by signs or symptoms consistent with hepatic injury (eg, new onset elevated PT/INR);
 - Two sequential AST or ALT elevations >5 times ULN, regardless of total bilirubin or accompanying signs or symptoms.

NOTE: In each case, there is a need for additional investigations, such as review of ethanol, recreational drug and dietary supplement consumption; testing for acute hepatitis A, B or C infection and biliary tract imaging should be promptly discussed with the sponsor or designee.

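### Section 7.1 removes from the study anyone who permanently stops drug, which contradicts 7.2.1 and is worded against the 28-day safety follow-up in 8.3.1

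*Protocol*

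**What the plan says.** Protocol Section 7.1 names the criteria in 10.8.2 as reasons for permanent discontinuation of study intervention. It then sets a rule with no stated limit: "If study intervention is definitively discontinued, the participant will not remain in the study for further evaluation".

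Section 7.2.1 reads: "Participants who request to discontinue receipt of study intervention will remain in the study and must continue to be followed for protocol-specified follow-up procedures". Its only exception is a participant who withdraws consent for further contact.

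Section 10.8.2 opens its list of AE, ECG and laboratory criteria with "Treatment will be discontinued and the participant withdrawn from this study for". On laboratory values it adds: "All the following laboratory abnormalities require discontinuation if they are confirmed by retest".

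Section 7.2, on leaving the study, contains two sentences that pull apart. One refers the site to the schedule of activities "for assessments to be collected at the time of study discontinuation and follow-up and for any further evaluations that need to be completed". Against this, the other says: "The participant will be permanently discontinued both from the study intervention and from the study at that time".

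Section 8.3.1 sets active AE and SAE collection for every participant, from consent "through and including a minimum of 28 calendar days, after the last administration of the study intervention". It names two early ends. One is screen failure. The other applies when a participant "withdraws from the study and also withdraws consent for the collection of future information, the active collection period ends when consent is withdrawn". It also says that investigators need not go looking for events once participation has concluded.

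The SoA marks AE monitoring in both the follow-up call column and the ET column. Footnote n gives the call to participants without exception.

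**The concern.** Two adjacent sections give opposite instructions about the same person. Either 7.1 is meant more narrowly than it reads, or it overrides 7.2.1; the protocol does not say which.

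What is at stake is safety follow-up. A site that takes 7.1 at its word could treat the ET visit as the last contact and never ask about events that begin in the following weeks. Section 2.3.1 lists infection, including serious and opportunistic infection and viral reactivation, as a potential risk of ritlecitinib. Participants stopped under 10.8.2 are among those in whom late events would be of most interest.

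**Working it through.** The plan gives no figure on this point. The check is a comparison of the texts, followed by a short calculation of size.

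**1. The conflict between 7.1 and 7.2.1.** Take a participant who, midway through Period 2, asks to stop ritlecitinib for good and is content to be telephoned.
- Under 7.1, drug is definitively discontinued, so the participant leaves.
- Under 7.2.1, the participant asked to stop and did not withdraw consent for contact, so the participant stays and must be followed.

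Both rules apply and neither yields to the other. Confining 7.1 to the 10.8.2 stops would remove the clash. But 7.1 says only that the reasons include those in 10.8.2, and the disputed sentence carries no limit.

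**2. Participants stopped under 10.8.2.** The texts that keep safety follow-up going are:
- 8.3.1, where withdrawal from the study ends collection early only if consent is withdrawn as well;
- 7.2, which sends the site to the SoA for follow-up;
- SoA footnote n, which exempts nobody from the call;
- the notes within 10.8.2, which continue lymphocyte subset testing until the count resolves or stabilizes and call for further investigation of liver cases.

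The texts worded against it are:
- 7.1 itself;
- the opening line of 10.8.2;
- the sentence in 7.2 that ends study participation at once;
- the release in 8.3.1 once participation has concluded. Section 4.4 defines completion, but no section says when participation concludes for someone withdrawn.

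The SoA does not say whether a participant who has an ET visit also receives the call.

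**3. What could be missed per participant.** Assume that the ET visit falls 0 to 2 days after the last dose. This fits the schedule. A Period 2 Day 9 safety laboratory sample with same-day results, plus a 24 to 48 hour retest (10.8.1), gives confirmation on Day 10 or 11. That is 1 to 2 days after a last dose on Day 9, or 0 to 1 day after one on Day 10.
- Window left after the ET visit: 28 − 2 = 26 days to 28 − 0 = 28 days.
- Completers are discharged on Day 12, 2 days after the Day 10 dose. Their gap before the call is 28 − 2 = 26 to 35 − 2 = 33 days.

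Completers also go about four weeks or more without scheduled contact, so the real difference is the call itself.

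**4. How many participants.** The protocol gives no stopping rate for this design. I assume a range of 1% to 2/48 = 4.2%. The upper value is the number in the ritlecitinib arm of the alopecia areata study who discontinued for treatment-emergent AEs (Section 2.2.4.2.3). That study treated patients for an initial 24 weeks, so 4.2% is likely high for 10 days in healthy participants. The 1% is purely an assumption.
- Expected number of 12: 12 × 0.01 = 0.12; 12 × 2/48 = 0.5.
- Chance of at least one: 1 − 0.99^12 = 11.4%; 1 − (46/48)^12 = 40.0%.

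**5. Effect on the analyses.** The last tolbutamide sample is due 36 hours after dosing, weeks before the call, so a missed call cannot alter the PK estimates. Section 10.3.1 requires a laboratory abnormality that leads to discontinuation from the study to be recorded as an AE. Participants stopped for an AE or a laboratory value therefore already count in overall AE incidence.

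**The case against.** The strongest reply is that 8.3.1 settles the matter. It covers every participant and treats withdrawal from the study and withdrawal of consent as separate events, with only the two together ending collection. On that reading, the release once participation has concluded refers to the time after the collection period; using it to shorten the period would defeat the explicit rule in the same section. The notes in 10.8.2 show that withdrawal is not the end of contact. Section 8.2.4 covers clinically significant laboratory values up to 28 days after the last dose, and 8.3.3 requires known events to be followed. The clash between 7.1 and 7.2.1 is also narrow: it bites only when a participant asks to stop permanently.

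Most of this stands. A reader might infer from 7.1 and 10.8.2 that the protocol deprives participants stopped for harm of their safety follow-up. The documents do not support that. For these participants the better reading is that the 28-day collection and the call apply, and known events remain covered in any case.

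The wording itself is not answered. Section 7.1 is unqualified, it contradicts 7.2.1 outright for one class of participant, and a site has to reconcile several sections to reach the right answer. Section 7.2 adds that incomplete withdrawal procedures are not deviations provided safety was preserved. If a site counted the call among those procedures, its omission might not be recorded.

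**Conclusion.** Section 7.1 is wrong as written: it contradicts 7.2.1 for a participant who asks to stop permanently while still consenting to contact. For participants stopped under 10.8.2, the required follow-up exists in 8.3.1 and footnote n, but 7.1, 7.2 and 10.8.2 are worded against it, and the relation between the ET visit and the call is unstated.

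Severity is minor. The possible loss is one telephone contact per affected participant, in an expected 0.1 to 0.5 of 12. These counts cover harm-based stops only and rest on the assumed rates; voluntary stops would add to them by an amount the documents do not allow me to estimate. The primary PK analysis is unaffected. The conflict in the text depends on none of these assumptions.

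**What to change.** Make four wording changes:

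- **7.1:** replace the disputed sentence with: *A participant who permanently stops study intervention receives no further dosing; unless consent for further contact is withdrawn, the ET assessments, active AE collection for at least 28 days after the last dose (Section 8.3.1) and the 28-35 day telephone contact still apply.* This also settles that the call follows an ET visit.
- **10.8.2:** in the opening line, have the participant *withdrawn from further dosing, with safety follow-up per Sections 7.1 and 8.3.1*, in place of withdrawn from the study.
- **7.2:** to the sentence on permanent discontinuation from both intervention and study, add *except for safety follow-up per Section 8.3.1, unless consent for further contact is withdrawn*.
- **8.3.1:** state that participation concludes no earlier than the end of the active collection period.

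The stopping criteria and the right to withdraw consent do not change. The cost is the text of an amendment and at most one telephone call, already in the SoA, for each participant who stops early.
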